We will screen approximately 500 PLWH at the Infectious Disease Institute (IDI) clinic to arrive at a sample of 96 participants who will be randomized to intervention or wait-list control (each evenly stratified by gender). There will be 4 gender-specific intervention groups and one control. The intervention consists of 6 workshops, which will occur approximately every other week. Participants will be asked to complete a workshop evaluation form after each workshop. Participants will be interviewed at baseline, 3-4 months after baseline, and again 6-7 months after baseline. The wait-list control will receive the intervention upon completion of the final follow-up assessment has been completed by all intervention groups.

Participants will be asked to recruit 1-3 of their social network members to participate in three interviews. We expect to screen approximately 180 social network members to arrive at 90 participants.

4. Methods

Screening/Recruitment

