The 6 workshops will be implemented over about three months. Each workshop will last about 2 hours and will be facilitated by 1-2 trained counselors with experience conducting group trainings and working with people living with HIV. The workshops will be administered in a group format to facilitate an interactive social process, social reinforcement, modeling, role-

plays and other interactive components of skills building; groups are most effective in developing self-identity as members of a community in which members rely on each other for support. A workshop evaluation survey will be conducted at the conclusion of each workshop.

PLWH interview and social network assessments will be conducted by trained IDI personnel. The interview and social network assessment both will be administered in a single session in either English or Luganda as preferred by the participant. The first interview will last approximately 2.5 hours, and the second two interviews will last approximately 2 hours.

The interviews will collect information about participant demographics; engagement with HIV care, prevention advocacy; knowledge/beliefs about and adherence to HIV medication; HIV-related self-efficacy; HIV status disclosure; discrimination and stigma; social support; physical and mental health status; alcohol use; and relationship status and sexual behavior. During the social network assessment portion, participants will be asked to list 20 adults (18+ years) with whom they have had contact within the preceding year (e.g., friends, family, other community members). We will collect first name and last initial for each social network member to avoid the potential for confusing individuals who might have the same first and last initial, and to assist with linking network member data across assessments (to assess network change over time). For each social network member listed we will collect information about demographics; perceived serostatus; description of the relationship between the PLWH participant and the individual; PLWH participant's engagement in prevention advocacy with the individual; social support provided by the individual; and the individual's expression of HIV-related stigma. We will also ask for a description of how often individuals listed in the social network assessment interact with each other.

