Workshop evaluation surveys will be administered to participants by IDI personnel at the end of each workshop to elicit data on usefulness of the workshop, comfort with specific exercises, and ideas for improvement. No identifying information will be collected in this survey.

Survey data will be entered into a spreadsheet and transmitted to RAND via SFTP. If onsite data entry is not possible, scanned copies of the surveys will be transmitted to RAND via SFTP. Any hardcopy files resulting from the survey will be retained by IDI.

5. Statistical Analysis

We will primarily use an intent-to-treat approach, with secondary analyses involving study completers. In addition to comparing the arms at each time interval, we will apply generalized mixed models (linear for continuous or ordinal outcomes; logistic for binary outcomes) to our repeated-measures data to examine how intervention effects change over time, using an indicator for study arm, an ordinal indicator of time, and time by arm interaction to indicate whether change differs between the arms.

Aim 1: To assess feasibility and acceptance of the intervention, we will examine recruitment (# who sign up as interested in participating each recruitment day) and retention, workshop attendance (# who attend all workshops), and participant feedback elicited in the process measures (ratings of benefit; recommendation to peers). We will also compare the characteristics of the participants with that of the larger clinic population using routine data collected by IDI in order to assess the degree of selection bias caused by our recruitment strategy.

Aim 2: To assess preliminary intervention effects on the outcomes (protective behavior of the HIV-positive clients: condom use, number of partners, engagement in HIV care, ART adherence), and diffusion of prevention messages across the network (content and extent of communication with network members about protective behaviors, including condom use, number of partners, HIV testing, engagement in HIV care, circumcision; HIV disclosure; and HIV stigma), we will primarily use an intent-to-treat approach, with secondary analyses involving

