study completers. In addition to comparing the arms at each time interval, we will apply generalized mixed models (linear for continuous or ordinal outcomes; logistic for binary outcomes) to our repeated-measures data to examine how intervention effects change over time, using an indicator for study arm, an ordinal indicator of time, and time by arm interaction to indicate whether change differs between the arms. A random-effects approach allows us to incorporate the heterogeneity among participants. We will use imputation for item nonresponse and account for non-random dropouts using logistic regressions that assign weights to retained participants that are inversely proportionate to the predicted probability of the participant being retained; if dropout is random, analyses will incorporate design effects when calculating standard errors and significance tests. With the intervention administered in groups, these analyses need to account for clustering of the data; however, the number of groups receiving the intervention is too small to reliably estimate the ICC to adjust standard errors; hence, we will use standard regression methods and explore the sensitivity of significance levels and conclusions to a range of plausible ICC values (.005 to .05) for the outcomes. We will also control for and examine interaction effects with intervention process variables (e.g., number of workshops completed), participant characteristics (e.g., ART status, gender, age), and alter characteristics (e.g., position in the network, HIV status, knowledge of ego's HIV status). This will enable us to address Aim 3, to explore the context of prevention advocacy, including differentiating types of alters who received more, versus less, prevention advocacy, as well as characteristics of participants who engaged in more prevention advocacy throughout the network, to a larger number of alters.

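### Neither Aim 2 analysis names the baseline value of the outcome as a covariate, so precision already paid for is given up

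*Combined protocol and SAP*

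**What the plan says.** Section 3 (Study Design) sets three assessments: "Participants will be interviewed at baseline, 3-4 months after baseline, and again 6-7 months after baseline". Section 4 (Methods, Procedures) shows that these interviews cover the outcome domains: "The interviews will collect information about participant demographics; engagement with HIV care, prevention advocacy; knowledge/beliefs about and adherence to HIV medication", followed by disclosure, stigma and sexual behavior. Baseline values of the participant-level outcomes are therefore collected.

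Section 5 (Statistical Analysis) describes the Aim 2 analyses in the general paragraph and again under Aim 2. There are two: "In addition to comparing the arms at each time interval, we will apply generalized mixed models", the models being linear for continuous or ordinal outcomes and logistic for binary ones, "using an indicator for study arm, an ordinal indicator of time, and time by arm interaction to indicate whether change differs between the arms". Clustering by workshop group is left to a sensitivity analysis: "hence, we will use standard regression methods and explore the sensitivity of significance levels and conclusions", over "a range of plausible ICC values (.005 to .05".

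The only covariates named are workshop process variables, "participant characteristics (e.g., ART status, gender, age" and alter characteristics. The next sentence gives the purpose of that list: "This will enable us to address Aim 3, to explore the context of prevention advocacy". The baseline value of the outcome appears nowhere as a covariate, and no constraint on the baseline arm means is stated.

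**The concern.** In a randomized comparison, the baseline value of an outcome is often the strongest available predictor of its later value, and conditioning on it removes variance from the treatment contrast. Neither planned analysis does this. The visit-by-visit comparison names no covariate. The mixed model has an unconstrained arm effect at baseline, so its interaction is a difference in change. That is less precise than adjustment at any correlation below 1, and less precise than ignoring baseline when the correlation is below 0.5.

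Preliminary effects are part of the primary objective, and they will be estimated from 96 people. Wider intervals than necessary weaken what the pilot can say. Leaving the covariate unnamed also leaves the choice to be made once the data are in hand.

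A smaller point concerns time. The plan calls it an ordinal indicator, which could mean visit categories or a 0/1/2 score. With a linear score, an effect present at 3-4 months and gone by 6-7 months gives a zero interaction.

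**Working it through.** **Inputs.** From the plan: 96 randomized; baseline and two follow-ups; 4 intervention groups; upper ICC .05. Not in the plan, so assumed: 48 per arm, two-sided 5%, effect 0.5 SD, no dropout, and baseline-to-follow-up correlation r = 0.3, 0.5, 0.7. The plan states no power or precision figure to reproduce.

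**Continuous outcome, one visit, SD 1.** Per-person variance factors:
- follow-up only: 1
- difference in change: 2(1 − r)
- baseline-adjusted: 1 − r²

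Since 1 − r² = (1 − r)(1 + r), the adjusted factor never exceeds 1 or 2(1 − r). An exact generalized least squares check (random intercept, three visits as categories) gives the mixed model as written factors of 1.40, 1.00 and 0.60, which equal 2(1 − r). Constraining the baseline means gives 0.91, 0.75 and 0.51, which equal 1 − r².

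The comparator below is always the better planned analysis. SE = √(2v/48); 95% half-width = 1.96 × SE; power = Φ(0.5/SE − 1.96); equivalent N = 96/ratio.

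| r | Better planned v | Adjusted v | Ratio | Equivalent N | Half-width (SD) | Power |
|---|---|---|---|---|---|---|
| 0.3 | 1.00 | 0.91 | 0.91 | 105 | 0.40 to 0.38 | 69% to 73% |
| 0.5 | 1.00 | 0.75 | 0.75 | 128 | 0.40 to 0.35 | 69% to 81% |
| 0.7 | 0.60 | 0.51 | 0.85 | 113 | 0.31 to 0.29 | 88% to 93% |

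Example at r = 0.5: SE falls from √(2/48) = 0.204 to √(1.5/48) = 0.177, so 0.5/SE rises from 2.45 to 2.83. The gain peaks at r = 0.5; the ratio is 0.96 at r = 0.2 and 0.90 at r = 0.8. A simulation of 20,000 trials gave ratios of 0.92, 0.76 and 0.86.

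**Other settings** (power at r = 0.3/0.5/0.7, better planned analysis to adjusted):
- ICC .05, 4 groups of 12, design effect 1 + 11 × 0.05 = 1.55 in the intervention arm only, group variance reduced in proportion: 58/58/80% to 62/71/86%
- Same ICC, group variance not reduced by adjustment: 58/58/75% to 61/68/79%
- Allocation 64:32: 64/64/85% to 68/76/90%
- 20% loss, 38 per arm: 59/59/80% to 63/71/86%

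**Binary outcome.** Simulated with 48 per arm, baseline prevalence 50%, follow-up 50% against 75%, and baseline-to-follow-up phi of 0.3, 0.5, 0.7. There were 10,000 trials for the two single-visit models. The random-intercept model had about 500 trials per setting, with Monte Carlo error of about 2 points.

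| Analysis | Power at phi 0.3 / 0.5 / 0.7 |
|---|---|
| Unadjusted comparison at the visit | 71 / 71 / 72% |
| Random-intercept time-by-arm test | about 61 / 69 / 82% |
| Logistic with baseline outcome | 75 / 81 / 90% |

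The standard error of the log odds ratio rises with adjustment, from 0.45 to 0.48, 0.54 and 0.68. Power still improves because the conditional odds ratio is a different and larger quantity. On the risk-difference scale the variance ratio is 0.95, 0.81 and 0.76 with this effect, and 0.92, 0.75 and 0.85 with none. With no effect the adjusted test rejects in 5.2%, 4.4% and 3.7% of trials. A separate simulation under a latent-normal model (about 50% against 76%, phi about 0.33, 0.49, 0.65) shows the same ordering: adjusted 80/85/89%, follow-up only 76/75/76%, difference in change 64/75/86%.

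**Time coding.** With scores 0, 1, 2, compound symmetry and complete data, the slope weights are −0.5, 0 and 0.5. The middle visit has no weight.

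**The case against.** The plan is a summary, its covariate list is open, and the list sits within the Aim 2 paragraph, so silence does not exclude baseline adjustment. That is fair. But the model is written out term by term, and followed as written it gives the less precise contrast.

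The mixed model does use baseline, and a difference in change is a valid analysis. This also stands: no result would be wrong. The issue is efficiency only.

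This is a pilot with no power claim, and the half-widths shrink by only 0.02 to 0.05 SD. The gain is indeed modest at low correlation, and the correlation is unknown, so only the range is supported. Against that, the plan intends to interpret significance levels, and the gain is free.

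Adjusted logistic models can fail when an outcome is rare. For 10% rising to 30%, about 3%, 11-14% and 38% of simulated trials at phi 0.3, 0.5 and 0.7 had non-convergence or a standard error above 5. The separation often concerns the baseline coefficient rather than the arm effect, and the power gain persists, but the plan should anticipate it.

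Some baselines will be missing: a newly listed network member has none, and adherence may be undefined for some participants. Covariate adjustment would drop these records, whereas a constrained-baseline model keeps them. The plan already imputes item nonresponse.

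On time coding, the wording does not require a linear score, and the planned visit-by-visit comparisons would still show a transient effect. That point is a clarification only.

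**Conclusion.** The concern holds. Both Aim 2 analyses as written leave out a covariate that is already collected. For continuous outcomes, adjustment reduces the variance by 9%, 25% and 15% at correlations of 0.3, 0.5 and 0.7 against the better planned analysis, and by more against the other one wherever the two differ. For binary outcomes it adds roughly 4 to 10 points of power in the setting examined, and precision only on the risk-difference scale. The direction for continuous outcomes follows from algebra at any correlation between 0 and 1. The sizes rest on the assumed correlation, effect, error rate and allocation, none of which the plan gives. Validity is not at stake, so this is a change worth making rather than one the trial depends on.

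**What to change.** In Section 5, Aim 2, name the baseline value of each outcome as a covariate, or constrain the baseline arm means to be equal in the repeated-measures model, with gender in the same model. Prefer the constrained form where baseline values may be missing, including network-member data. Report adjusted arm differences with intervals at 3-4 and 6-7 months.

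For binary outcomes, include the baseline outcome in the logistic model, report a standardised risk difference beside the odds ratio, and say what will be done if a sparse outcome causes separation. State that time enters as visit categories with arm-by-visit terms.

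The cost is wording and model code. Baseline interviews and gender are already collected, and the planned regression methods accept covariates.

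### Could the planned ICC sensitivity check miss workshop-group clustering in the time-by-arm test?

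*Combined protocol and SAP*

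**What the plan says.** All references are to the combined protocol and SAP.

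- **Layout (section 3).** The sample is 96 participants. "There will be 4 gender-specific intervention groups and one control".
- **Visits (section 3).** "Participants will be interviewed at baseline, 3-4 months after baseline, and again 6-7 months after baseline".
- **Workshops (section 4, Procedures).** "The 6 workshops will be implemented over about three months".
- **Control arm (section 3).** "The wait-list control will receive the intervention upon completion of the final follow-up assessment has been completed by all intervention groups".
- **Effect of interest (section 5).** The arms are compared at each time point. The repeated-measures models also carry a "time by arm interaction to indicate whether change differs between the arms".
- **Random effects (section 5, Aim 2).** "A random-effects approach allows us to incorporate the heterogeneity among participants". No random effect for workshop group is named.
- **Clustering (section 5, Aim 2).** "With the intervention administered in groups, these analyses need to account for clustering of the data". The plan then says that there are too few workshop groups for a reliable ICC estimate with which to correct standard errors. It therefore chooses ordinary regression and a commitment to "explore the sensitivity of significance levels and conclusions to a range of plausible ICC values (.005 to .05) for the outcomes".

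**The concern.** The sensitivity step is the plan's only allowance for workshop clustering, and it leaves two things open.

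**Timing.** The workshops fall between the baseline and follow-up interviews (the natural reading, though not stated outright), so clustering that they cause cannot exist at baseline. A common way to add a cluster to a mixed model is a group intercept with the same value at every visit. Such an intercept drops out of each participant's change from baseline, and so out of the time-by-arm term. The check would then call almost any time-by-arm result robust.

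**Arm.** Controls receive no workshops until follow-up is over, so only the intervention arm is clustered during the analysed period. A design effect applied to both arms would treat controls as clustered when they are not.

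At stake is whether a nominally significant time-by-arm result is reported as robust to clustering. If clustering appears only after baseline and the check cannot register it, the test's error rate exceeds the nominal 5% and nothing in the report shows it.

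**Working it through.** The documents give no power, alpha or clustering calculation, so there is no figure of theirs to reproduce.

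**Inputs from the documents:** 96 participants, four intervention groups, one control arm, three visits, ICC .005 to .05.

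**Assumptions:** 48 v 48; hence m = 48/4 = 12 per group; two-sided 5%; continuous outcome with variance 1; within-person correlation r = .3, .5, .7; complete data; normal reference distribution.

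**1. Constant group intercept.** Write a participant's outcome as group effect + person effect + error. In follow-up minus baseline, the group effect subtracts out. Generalised least squares with known covariance gives a time-by-arm SE ratio to the participant-only model of 1.0000 at ICC .005 and .05 for all three r. With 21% dropout at the last visit it stays within about 0.1% of 1. In logistic models fitted to 12 simulated datasets at ICC .05, the SE rose by 0.1% to 1.3% and z rose slightly on average (1.56 to 1.58), so there was no protection. A comparison of arms at one follow-up does respond: the SE rises by about 1.4% at ICC .005 and 13% to 14% at ICC .05.

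**2. Group effect after baseline, intervention arm only.** The variance of mean change is [2(1−r) + 11·ICC]/48 in the intervention arm and 2(1−r)/48 in the control arm. The SE multiplier is √{[4(1−r) + 11·ICC] / [4(1−r)]}.

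- ICC .05, r = .3: √(3.35/2.8) = 1.094
- ICC .05, r = .5: √(2.55/2) = 1.129
- ICC .05, r = .7: √(1.75/1.2) = 1.208
- ICC .005: 1.010, 1.014, 1.023

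At ICC .05 an unadjusted 5% test then has true error 2[1 − Φ(1.96/multiplier)] = 7.3%, 8.3%, 10.5%. If the group variance ICC/(1−ICC) is added on top of the total instead, the multiplier is √[1 + 3·ICC/((1−ICC)(1−r))]. At ICC .05 that gives 1.107, 1.147, 1.235, with error 7.7%, 8.8%, 11.3%.

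**3. Design effect on both arms.** The multiplier is √(1 + 11·ICC): √1.055 = 1.027 at ICC .005 and √1.55 = 1.245 at ICC .05. If the truth is step 2 at ICC .05, the error after this correction is 2[1 − Φ(1.96 × 1.245/multiplier)]:

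| r | Uncorrected | Both-arm design effect |
|---|---|---|
| .3 | 7.3% | 2.6% |
| .5 | 8.3% | 3.1% |
| .7 | 10.5% | 4.3% |

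Under the second convention the corrected figures are 2.8%, 3.3% and 4.8%.

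**4. Where the both-arm correction stops being conservative.** Set 11·ICC/[4(1−r)] = 11·ICC. Then 4(1−r) = 1 and r = .75, whatever the ICC. Under the second convention at ICC .05, 3 × .0526/(1−r) = .55 gives r ≈ .71. At r = .8 the design effect falls short (1.245 against 1.299).

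**5. How many results could be reclassified.** At ICC .05 an unadjusted p survives if it is below 2[1 − Φ(1.96 × multiplier)]. That is .05 with a constant intercept, .032 to .018 with the post-baseline effect (r = .3 to .7), and .015 with the both-arm design effect. Without the constant intercept, the last two disagree only between .015 and .018 to .032, and the design effect is the stricter.

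**The case for a change.** The best case for a change is that the sentence on clustering is complete yet silent on method. One plausible implementation would make the check empty for the very term used to judge differential change. A sentence or two would close the gap and prevent the form being chosen after the results are seen.

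Much of this stands. The plan does not say how the ICC enters, and the cancellation is exact in the linear case with complete data and near enough elsewhere. A further point also stands. If the analyst applies a design effect to the intervention arm alone and carries the single-visit factor over to time by arm, the multiplier at ICC .05 is √[(1.55 + 1)/2] = 1.129. That matches the post-baseline effect at r = .5 but is too small at r = .7, where the error is 2[1 − Φ(1.96 × 1.129/1.208)] = 6.7%, against 10.5% uncorrected.

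What does not stand is the step from silence to fault. The text treats the ICC as a standard-error correction alongside ordinary regression, which points away from a group random intercept. It also locates the clustering in the groups that get the workshops, so one-arm clustering is implied. Nor does a both-arm design effect always over-correct: for time by arm that depends on r. Lastly, comparisons at individual visits, also planned, respond even to a constant intercept.

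**Conclusion.** The concern identifies a missing detail, not an error. The empty version of the check requires a model that the plan does not describe. On the natural reading, a design effect on standard errors, the check moves the time-by-arm result by 2.7% to 24.5% in SE across the stated range. Against post-baseline clustering in one arm at ICC .05, the both-arm form keeps the error at 2.6% to 4.8% for r from .3 to .7. It turns mildly anti-conservative only above r of about .71 to .75. Corrections confined to the intervention arm are less protective at high r but still reduce the error.

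The practical reach is small. At ICC .005 the post-baseline effect adds only 1.0% to 2.5% to the SE. At ICC .05 the sensible versions disagree over a narrow band of p-values. The objectives (section 2) are feasibility, acceptability and preliminary effects, so at most the description of a preliminary signal would change. An analyst who knows that the workshops follow baseline and reach one arm only can apply the ICC sensibly without an amendment.

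These figures rest on 48 v 48, 12 per group, a two-sided 5% level, r of .3 to .7 and a normal reference, none of which the plan states. The error rates are for continuous outcomes; for logistic models there is only the small simulated check.

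### The Aim 2 paragraph calls for adjustment for number of workshops completed, and no sentence keeps this post-randomisation variable out of the between-arm intent-to-treat models

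*Combined protocol and SAP*

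**What the plan says.** Section 5 states the Aim 2 principle as "HIV disclosure; and HIV stigma), we will primarily use an intent-to-treat approach", with completer analyses second. The effect model is a mixed model with "an indicator for study arm, an ordinal indicator of time, and time by arm interaction". By-visit contrasts are planned alongside it: "In addition to comparing the arms at each time interval". No covariates are named for either.

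After dealing with dropout and clustering, the same Aim 2 paragraph adds: "We will also control for and examine interaction effects with intervention process variables (e.g., number of workshops completed". Participant characteristics and alter characteristics follow in the same list. The next sentence reads: "This will enable us to address Aim 3, to explore the context of prevention advocacy".

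Three other statements bear on the variable:

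- Section 5, Aim 1, treats attendance as a feasibility result: "workshop attendance (# who attend all workshops".
- Section 3 (Study Design): "The wait-list control will receive the intervention upon completion of the final follow-up assessment has been completed by all intervention groups".
- Section 4 (Methods, Procedures): "The 6 workshops will be implemented over about three months". Section 3 places the follow-up interviews at 3-4 and 6-7 months after baseline.

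**The concern.** Number of workshops completed is listed next to age and gender as if it were the same kind of covariate. It is not. It is determined after randomisation, it can be affected by the same traits that affect the outcomes, and in the control arm it is zero for everyone at every between-arm assessment.

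An analyst who applies the adjustment literally to a between-arm model would report an arm coefficient that compares intervention participants, extrapolated to zero workshops, with controls. That coefficient loses whatever benefit attendance carries, can be biased in either direction if attendance is related to prognosis, and is much less precise. Section 2 (Objectives) makes preliminary intervention effects part of the primary objective, so a mislabelled estimate would affect a main result of the pilot.

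**Working it through.** The documents give no effect size, attendance rate or variance, so there is no stated figure to reproduce. The check has a structural part, which needs no assumptions, and an illustration of size, which does.

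**Structure.** For controls W (workshops completed) = 0, so arm × W = W for every participant. The design matrix [1, arm, W, arm × W] has 4 columns and rank 3, so an arm-by-workshops interaction cannot be identified. With arm and W both in the model, the arm coefficient is the contrast at W = 0.

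**Inputs.** From Section 3: 96 participants, 6 workshops, four intervention groups and one control. Assumed: outcome SD 1; true effect 0.5 SD at both follow-ups; attendance a = 0.8; beta-binomial correlation between a person's attendances rho = 0.2; within-person outcome correlation 0.5; allocation 48:48, because no ratio is stated, or 77:19 if five groups are of equal size (96/5 = 19.2). Let d be the share of benefit carried by attendance and r the attendance-outcome correlation through prognosis.

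**Single visit, adjusted for W.**

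- Mean m = 6a = 4.8; variance s² = 6a(1-a)(1+5·rho) = 0.96 × 2 = 1.92; m/s = 4.8/1.386 = 3.46.
- Within-arm slope on W = 0.5d/m + r/s, so adjusted arm = 0.5(1-d) - r·m/s.
- With r = 0: 0.50, 0.25, 0.00 for d = 0, 0.5, 1.
- With d = 0 and r = +0.2 / -0.2: 0.5 ∓ 0.69 = -0.19 / 1.19.
- The same at 60% attendance: m/s = 3.6/1.70 = 2.12, giving 0.08 / 0.92. At 90%: m/s = 5.4/1.04 = 5.20, giving -0.54 / 1.54.

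**Precision.** Variance inflation for arm = 1 + (1-p)m²/s², with p the intervention share. At 48:48: 1 + 0.5 × 12 = 7.0. At 77:19: 1 + (19/96) × 12 = 3.4. At 48:48 the unadjusted SE is √(2/48) = 0.20 and the adjusted SE is 0.204 × √7.0 = 0.54. In 5,000 simulated trials of 96 the adjusted SD was 0.55-0.58.

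**Mixed model** (random intercept, three visits, visit categorical, true effect 0, 0.5, 0.5). The result depends on how W is coded, which the plan does not state.

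- *Fixed total per person.* The fitted slope averages the three visits. At d = 1, r = 0, slope × m = (0 + 0.5 + 0.5)/3 = 0.33. The arm contrast is then -0.33 at baseline and 0.17 at the last visit, but time by arm is 0.17 + 0.33 = 0.50, unchanged. At d = 0, r = +0.2 / -0.2, the last-visit contrast is -0.19 / 1.19 and time by arm is again 0.50. The SE of the last-visit contrast is 0.46 against 0.20.
- *Workshops to date* (0 at baseline, total at both follow-ups). At r = 0, time by arm is 0.50, 0.25, 0.00 for d = 0, 0.5, 1. At d = 0, r = +0.2 / -0.2, it is 0.15 / 0.85. The SE is 0.41 against 0.20.

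**Second check under other assumptions** (2,000 simulated trials per setting, 48:48, attendance probability 0.8, a motivation trait driving attendance). An effect of 0.46 SD carried wholly by workshops fell to 0.00 after adjustment, and power fell from 60% to 5%. With no true effect and motivation correlated 0.3 with the outcome, the adjusted estimate was -0.68 SD and false rejection 25%, against 5% unadjusted.

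**The case against.** The text leans away from the harmful reading. The effect model is set out twice in Section 5 with the same three terms, and workshop count is in neither. The disputed sentence comes after the model, dropout and clustering have been covered, and its stated purpose is Aim 3. Its list includes alter characteristics, which do not fit naturally into a participant-level model for ART adherence or condom use, so it reads more like a menu for exploratory models than a covariate set for every Aim 2 model. The non-identifiable interaction also suggests that a dose analysis was meant. Finally, under the simplest coding, one total per person, the time-by-arm term is untouched.

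Most of this stands, and it limits the point. A reader might infer that the sponsor has committed to adjusting the intent-to-treat analysis for attendance, or that the reported effect will be distorted. The documents support neither: the listed model does not contain the variable.

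The objection does not close the gap. A sentence of purpose is not a restriction. The adjustment is stated inside the Aim 2 paragraph as a continuation of those analyses, and nothing confines it to Aim 3, to the intervention arm or to separate models. The by-visit contrasts, where a fixed total does its damage, have no stated covariate set.

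**Conclusion.** The point holds as an open ambiguity that should be fixed. The listed arm, time and time-by-arm model is sound and suffers only if workshop count is added. If it is added, the arm term is not the intent-to-treat effect and an arm-by-workshops interaction cannot be estimated; neither statement depends on any assumed number.

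The size does depend on assumptions. At 80% attendance and rho 0.2, a true 0.5 SD by-visit effect could appear as anything from 0.50 down to 0.00 according to mediation alone, or as -0.19 to 1.19 under a prognostic correlation of ±0.2. Over 60-90% attendance, that last pair widens from 0.08 / 0.92 to -0.54 / 1.54. Harm to the time-by-arm term requires a time-varying coding that the plan does not mention. This is a pilot with no confirmatory claim, which lowers the stakes but does not remove them.

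A reader might also infer from the same list that Aim 2 effects will be adjusted for alter characteristics measured at follow-up. The documents do not say so, and that is not part of this point.

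**What to change.** In Section 5, Aim 2, state that intervention effect estimates, both the by-visit comparisons and the mixed models, come from models containing only arm, time, arm by time and baseline covariates. Remove the commitment to adjust for process variables in any between-arm model. Assign workshop dose to Aim 3 as an exploratory, non-randomised analysis, for example within the intervention arm.

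The cost is a wording change to the SAP; no new data are needed. The downside is that the dose analysis will be small and confounded by who chooses to attend, and it should be reported as such.
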